### 8.3.1.1 Methodology for analysing the acute procedural success rate

Acute procedural success rate will be reported as frequency and percentages. Acute procedural success rate by patients will be calculated as number of patients with acute procedural success divided by number of patients with an attempted Phased RFA procedure. Acute procedural success rate by vein will be calculated as number of veins with electrical isolation verified divided by number of veins attempted with Phased RFA. 95% confidence intervals will be calculated using Fisher's exact method.

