4.3 Sample size considerations

The sample size determination has been based on chronic efficacy, freedom from AF recurrence at 12 months. The sample size calculation is based on the main objective to document real-life mid-term efficacy of patients with atrial fibrillation who have undergone Phased RFA. Efficacy in this case is assumed as the proportion of AF recurrence within 12 months following the index procedure.

The table below shows the sample size needed for estimating a binomial proportion for given prevalence with corresponding precision.

Table 4-1: Table for precision and prevalence for sample size assessment.

| Prevalence | Precision | | | |
|------------|-----------|------|-----|-----|
| | 1% | 2.5% | 5% | 10% |
| 0.1 | 4150 | 665 | 167 | 42 |
| 0.2 | 7377 | 1181 | 296 | 75 |
| 0.3 | 9682 | 1550 | 388 | 98 |

Precision = half-width of a 95% Confidence Interval (CI)

Design effect = 1.2 (variance inflation due to cluster sampling design)

Low sampling rate assumed to have no impact on sample size calculation

Assuming a prevalence of 20% of re-ablations 12 months after treatment, a sample size of 800 will allow the study to estimate the prevalence with a given precision of $\pm 3.8\%$ [range of 95%-CI: 7.6%]. This size guarantees enough information for estimating the prevalence in smaller subgroups (e.g. subgroup with a prevalence of 25% with a precision of $\pm 6.6\%$ [range of 95%-CI: 13.3%]).

A drop-out rate of 25% is assumed, i.e. an estimated drop-out rate of 200 patients. Therefore, it is planned to enroll a total number of patients of approximately 1000.

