In previous studies with Phased RFA an average acute procedural success of 98.2% (93-100%) was reported in patients with paroxysmal AF (23 studies). This is similar to the average acute procedural success reported for patients (6 studies) with persistent AF of 96.3%. In the case of index procedural failure, the authors linked the failure to the patient anatomy or characteristics and not to the Phased RFA system.

Endpoint definition:

- Procedure attempt was not declined due to technical issues related to Phased RFA system
- Only PVAC catheter(s) used to achieve PVI
AND
- All accessible PVs were isolated (entrance and/or exit block confirmation per vein)

If exit or entrance block was not verified during the procedure the data will not be used for this analysis.

Analysis Method: Acute procedural success rate will be reported as frequency and percentage at both the patients and vein level. Acute procedural success rate by patients will be calculated as number of patients with acute procedural success divided by number of patients with an attempted Phased RFA procedure. Acute procedural success rate by vein will be calculated as number of veins with electrical isolation verified divided by number of veins attempted with Phased RFA. 95% confidence intervals will be calculated using Fisher's exact method.

Limitation: Even though PVAC GOLD catheter has been designed anatomically, steerability can be influenced by the sheath used with the catheter. With fixed curve sheath might become challenging to reach all PVs, in particular right inferior PV due to technical issues. Due to this additional use of 3D system and irrigated catheters might be utilized by the medical centers where steerable sheath is not available.

Assess Phased RFA efficiency

Rational: The multi electrode catheter technology delivers continuous lesions and shortens procedure times. The ability to map and ablate with the same electrode simplifies and shortens the procedure.

Procedure duration is impacted by the maneuverability of the catheter. The new catheter design of the PVAC GOLD array allows enhanced tissue contact due to the 20° forward tilt.

Hospital resource allocation is another indicator of procedural efficiency, reflected by the procedure duration ("from skin to skin"), laboratory occupancy ("from door to door"), fluoroscopy time as well as number of used catheters and adjunctive devices (mapping and navigation) used.

Endpoint definition:

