# 8 Descriptive Statistics

This section describes the most relevant parts of the statistical analyses planned for this registry. All planned statistical methods will be described in detail in the Statistical Analysis Plan, which should be finalized prior to interim analysis and need to be finalized prior final analysis.

In general, this registry is intended to collect data under real life conditions. The statistical analysis will be performed in explorative and descriptive manner, i.e. no pre-specified hypothesis testing.

All variables collected in the CRF as well as the data obtained from the QoL assessments and all derived parameters will be used in the statistical analysis.

Binary, categorical, and ordinal parameters will be summarized by means of absolute and percentage numbers within the various categories.

Continuous data will be summarized by means of standard statistics, i.e. number of available data, number of missing data, mean, standard deviation, minimum, median, maximum, 5th and 95th percentile, lower and upper quartile (see SAP Appendix A).

Time-to-event data is planned to be analysed via a Cox proportional hazard regression model presenting hazard ratios and the corresponding 95% CI. In addition, Kaplan-Meier

curves may be presented for the time-to-event data. Two-sided 95%-CI will be presented for important parameters, but should be interpreted in an exploratory descriptive way. No formal statistical tests are planned within the statistical analysis. Event rates will be calculated for 3, 6, 9 and 12 months after first documented procedure and may be displayed graphically.

To measure statistical differences in continuous or dichotomous/ multinomial variables between baseline and 12 month FU non-parametric (e.g. Friedman's Chi-Square Test, McNemar's Test) will be utilized. The test is only performed if the variable is not missing at admission and discharge.

A biometrical report including descriptive statistics of all relevant documented parameters will be generated for the overall patient population as well as for each participating country (SAP chapter 8.7). Depending on the variable(s) of interest, additional selection criteria for subjects (e.g. subgroup analyses) considered in specific analyses may be used, if considered useful during the statistical analysis (SAP chapter 8.6).

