### 8.3.1 Characterize the acute procedural success rate

Success rates will be calculated for all documented procedures combined (patient level). Also, procedure success rates will be provided for first documented procedures, additional procedures, regular cases and training cases, separately. Success rates will also be shown per vein.

Success will be calculated for procedures that have been attempted (number of RF applications per patient > 0). Success rates will be provided for PVAC GOLD solely procedures (ancillary objective) and additionally for not PVAC GOLD solely procedures (using other catheter and/or using adjunctive devices).

If RF applications per patient, consumables (Phased RFA catheters used), successfulness and PV confirmation (exit or entrance block) was not verified for the procedure, the data will not be used for analysis. Consumables and procedure success will be taken from the procedure form. Relatedness of Phased RFA will be taken from AE form.

The procedure is considered successful if:

- Procedure attempt was not declined due to technical issues related to Phased RFA system and
- Only PVAC catheter(s) used to achieve PVI and
- All accessible PVs were isolated (entrance and/or exit block confirmation per vein)

This combined endpoint (variables linked via “and operation”) is applicable, if all conditions are available and complied.

Because of different procedure forms (eCRF V1.3 and eCRF V1.4), PVI achievement by PVAC GOLD only is assumed for patients documented by eCRF V1.3 as follows:

- [F21000010] Phased RFA catheter used: only PVAC GOLD is ticked, and
- [F22000010] to [F22000060] PVI confirmation: exit block and/or entrance block are ticked, and
- [F20001000] Number of RF applications per patient > 0

Unsuccessfulness per vein is considered, if the vein is not isolated or not verified. Percentages for success will be shown per vein for patients treated with PVAC GOLD solely. Precondition is that the number of RF applications per patient is greater than zero.

PVI achievement by PVAC GOLD only is defined for patients documented by eCRF V1.4 as follows:

- [F21000010] Phased RFA catheter used: only PVAC GOLD is ticked, and
- [F22000062] Where all PVs isolated at the end of the procedure = yes, and
- [F22000066] Where all PVs isolated by using PVAC only = yes, and
- [F21000010] Number of RF applications per patient > 0

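### The exact binomial interval for the pooled per-vein success rate ignores that a patient's veins are correlated, so its 95% limits are somewhat too narrow

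*SAP*

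**What the plan says.** Protocol 4.4.3 sets two levels of reporting for acute procedural success: "Acute procedural success rate will be reported as frequency and percentage at both the patients and vein level". SAP 8.3.1.1 defines the vein-level rate as "number of veins with electrical isolation verified divided by number of veins attempted with Phased RFA". The numerator and denominator are sums over all patients, so the unit of analysis is the vein.

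One interval method follows, for both levels: "95% confidence intervals will be calculated using Fisher's exact method". I read this as the Clopper-Pearson exact binomial interval. SAP 8 adds that "Two-sided 95%-CI will be presented for important parameters" and that these are to be read in an exploratory, descriptive way.

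I found no adjustment in either document for several veins coming from one patient. The only allowance for clustering is the design effect of 1.2 in Protocol 4.3 and SAP 3.3, described as "variance inflation due to cluster sampling design". It belongs to the sample size for the main objective.

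**The concern.** An exact binomial interval has its stated coverage when the trials are independent. SAP 8.3.1 lists six confirmation fields per procedure (F22000010 to F22000060), so a patient normally contributes several veins. Protocol 4.4.3 reports that authors of earlier studies attributed failed index procedures to patient anatomy or characteristics, and it says that the sheath used can make some veins hard to reach. All veins treated in one procedure share both factors. Positive correlation is therefore the natural expectation, and under it the pooled rate carries less information than its vein count suggests.

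What is at stake is the label on the interval. In a descriptive registry the estimates and intervals are the result, and SAP 8.4 allows this objective to be calculated at the interim analysis and used for publication. The affected quantities are:

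- the pooled vein rate;
- contrasts of that rate between different patients, such as PVAC GOLD solely versus not;
- vein rates computed over combined procedures, where one patient can contribute the same vein more than once.

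**Working it through.** The plan gives no width, limits or vein count for this interval, so there is no figure of its own to reproduce.

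**Inputs**

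- Patients: N = 1000 (Protocol 4.3, planned enrolment). The 800 patients on which the precision statement rests give similar results.
- Success rate: p = 98.2%, from Protocol 4.4.3: "average acute procedural success of 98.2% (93-100%) was reported in patients with paroxysmal AF". The protocol does not say whether this is per patient or per vein, so it is illustrative. The persistent AF figure of 96.3% is used as a second value.
- Veins per patient: m = 4. This is an assumption, with 3 and 5 as the range.
- Within-patient correlation: not given. Assumed range 0 to 0.5.

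**Formulas**

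- DEFF = 1 + (m − 1) × ICC
- Effective sample size = N × m / DEFF
- Interval as planned: Clopper-Pearson on N × m = 4000 veins
- Adjusted interval: Clopper-Pearson on the effective sample size
- Coverage of the planned interval: beta-binomial simulation
- Hand check on coverage: 2Φ(1.96/√DEFF) − 1

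**Results for p = 98.2%, m = 4, N = 1000**

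The planned interval is 97.74 to 98.59%, total width 0.85 points.

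| ICC | DEFF | Effective n | Adjusted interval (%) | Width (points) | Simulated coverage | Hand check |
|---|---|---|---|---|---|---|
| 0 | 1.0 | 4000 | 97.74–98.59 | 0.85 | about 96% | 95.0% |
| 0.02 | 1.06 | 3774 | 97.72–98.60 | 0.88 | about 95% | 94.3% |
| 0.05 | 1.15 | 3478 | 97.70–98.62 | 0.91 | about 94% | 93.2% |
| 0.1 | 1.3 | 3077 | 97.67–98.64 | 0.97 | about 92% | 91.4% |
| 0.2 | 1.6 | 2500 | 97.60–98.68 | 1.09 | about 89% | 87.9% |
| 0.3 | 1.9 | 2105 | 97.54–98.72 | 1.19 | about 86% | 84.5% |
| 0.5 | 2.5 | 1600 | 97.42–98.79 | 1.37 | about 80% | 78.5% |

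The hand check runs a point or two below the simulation because it ignores the slight conservatism of the exact method. That conservatism absorbs an ICC of about 0.02 and is used up by 0.05.

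**Sensitivity**

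- At p = 96.3% (N = 1000, m = 4), coverage is 92.7%, 88.5%, 86.0% and 78.9% at ICC 0.1, 0.2, 0.3 and 0.5.
- At ICC 0.3 and p = 98.2%, coverage is about 90% with 3 veins per patient and about 83% with 5.
- The extra total width is 0.97 − 0.85 = 0.12 points at ICC 0.1 and 1.37 − 0.85 = 0.52 points at ICC 0.5, which is about 0.06 to 0.26 points per side.

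**Differences between veins of the same patients**

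Here the variance is V1 + V2 − 2Cov. With equal variances V and correlation ICC it is 2V(1 − ICC), so the true SD is √(1 − ICC) times the value under independence: 0.95, 0.84 and 0.71 at ICC 0.1, 0.3 and 0.5. Ignoring the correlation overstates the uncertainty of such a difference.

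**The case against.** The strongest reply has five parts.

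1. **The effect may be nil or trivial.** No correlation is given, and the interval is valid up to about 0.02. Protocol 4.4.3 also points to a cause specific to one vein: the right inferior vein is hard to reach with a fixed-curve sheath. An ICC of 0.5 would mean that, given one failed vein, each other vein of that patient fails with probability 0.5 + 0.5 × 0.018 = 0.51, which is extreme. This stands as a reason to show the whole range and not to rely on its upper end. It does not make zero correlation the expected case.

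2. **The rate may be tabulated by named vein.** SAP 8.3.1 says that success will be shown per vein. For one named vein at first procedures each patient contributes once, and within-patient clustering disappears. That is correct and limits the point. The definition in SAP 8.3.1.1 still describes a pooled rate.

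3. **A reader might infer that differences between veins look too certain.** The documents do not support that. Those veins are paired within patients, and the calculation above shows the opposite direction. Overconfidence applies only to the pooled rate and to contrasts between different patients.

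4. **A reader might take the 1.2 design effect as an admission that veins need adjustment.** It refers to the cluster sampling design for the main sample size and says nothing about veins within patients. Any clustering by site or operator is a separate matter and is not addressed here.

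5. **Nothing depends on the interval.** The objective is ancillary, no hypothesis or threshold is attached, and the shift is a fraction of a percentage point. This stands, and it sets the severity.

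**Conclusion.** The point holds in a limited form. As written, the pooled vein rate gets an interval that requires independent veins, with nothing elsewhere to correct it, and the protocol's own account of failures makes positive correlation likely. Under the stated assumptions (4 veins, 1000 patients, 98.2%), coverage falls from a valid 95 to 96% at ICC 0 to 0.02 to about 92% at 0.1 and about 80% at 0.5. The missing total width is roughly 0.1 to 0.5 percentage points.

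The direction needs only more than one vein per patient and an ICC above the small amount that the exact method absorbs. The size depends on an ICC that the documents do not give. The patient-level rate at first procedures and single-vein rates at first procedures are not affected. Severity is low.

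**What to change.** Amend SAP 8.3.1.1 along these lines:

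- Keep the exact binomial interval for the patient-level rate.
- For the vein rate pooled over veins, or over combined procedures, use an interval clustered on patient. Preferred is a Clopper-Pearson interval on the effective sample size n/DEFF, with DEFF estimated from the data as the ratio of the patient-clustered variance to the binomial variance. GEE or a patient-level bootstrap is acceptable where there are enough failures.
- Where a stratum has no failures, DEFF cannot be estimated and GEE or the bootstrap degenerates. Fall back there on the plain exact interval with the patient as the unit.
- State whether the by-vein rate is pooled, tabulated by named vein, or both. For a named vein at first procedures the plain exact interval can stay.

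This takes a short SAP amendment and a few lines of SAS, and it uses data already collected. The price is a slightly wider interval.

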### 8.3.2 Assess Phased RFA efficiency

Phased RFA efficacy data will be shown for all documented procedures combined (patient level). Also, phased RFA efficacy will be provided for first documented procedures, additional procedures, regular cases and training cases, separately.

The parameters to measure the efficiency:

- Procedure duration
- Laboratory occupancy duration
- Fluoroscopy time
- Phased RFA consumables used
- Adjunctive devices (mapping or navigation systems)

**Table 10:** Phased RFA efficiency variables from procedure form

Objective section	Definition (used variables)	Related FID's annotated CRF (V1.3, V1.4)
Procedure duration	General time of the procedure	F20000611
Laboratory occupancy duration	Time patient delivered to the Catheter Lab Time patient left the Catheter Lab	F20000420 F20000610
Fluoroscopy time	Total fluoroscopy time	F20000620
Phased RFA consumables used	General number of catheters used Phased RFA catheters used Other (free text field)	F21000005 F21000010 F21000020
Adjunctive devices (mapping or navigation systems)	Adjunctive devices used during the procedure Other (free text field)	F21000040 F21000050

Phased RFA efficiency will be analysed for all implemented procedures only (number of RF applications per patient > 0). Time data will be shown for PVAC GOLD solely and using different catheters or adjunctive devices. Additionally, it will be distinguished between reasons of ablation (index, repeated, re-ablation, left Afl).

### 8.3.3 Characterize the peri-procedural anticoagulation therapy

Peri-procedural anticoagulation therapy data will be shown for all documented procedures combined (patient level). Also, peri-procedural anticoagulation therapy will be provided for first documented procedures, additional procedures, regular cases and training cases, separately.

The parameters of interest:

- Activated clotting time (ACT) during the procedure
- Peri-procedural INR
- Oral anticoagulant therapy/LMWN before, during and after the procedure
- TIA/stroke related to study Phased RFA procedure

**Table 11:** Peri-procedural anticoagulation therapy variables from baseline, procedure and AE form

Objective section	Definition (used variables)	Related FID's annotated eCRF (V1.3, V1.4)
Activated clotting time (ACT) during the procedure	Highest ACT during procedure Lowest ACT during procedure	F20000300 F20000320
Peri-procedural INR	Latest measured INR INR value Date of INR test	F20000260 F20000270 F20000280
Oral anticoagulant therapy/LMWN before, during and after the procedure	Procedure form: Was oral anticoagulant discontinued before the procedure How many hours prior to procedure Was LMWH administered before the procedure Instead of oral Anticoagulants In addition to the oral anticoagulants  Baseline form (prior procedure): Anticoagulation Medication Specify (free text field)  Procedure form (after procedure): Was anticoagulation continued after the procedure How long after procedure  Procedure form (after procedure/at discharge): Anticoagulation Medication Specify (free text field)	F20000210 F20000220 F20000230 F20000240 F20000250 F17500100 F17500120 F23000060 F23000070 F19500100 F19500120

TIA/stroke related to study Phased RFA procedure	Procedure form: Date of procedure Phased RFA procedure successful? No – Due to AE  AE form: Date of AE	F20000010 F22000180 F22000190  F30000010 F31000010_2 F31000010_3
---	--	--

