Rational: Two known complications that occur during or shortly after the procedure: thromboembolic events including stroke and major bleeding including cardiac tamponade, with an estimated incidence of 1.33% and 0.94%, respectively (23). The combination of heightened risk of both stroke and hemorrhage is linked to the complexity of the AF ablation procedure and the need for adequate peri-procedural anticoagulation. Historically, peri-procedural warfarin therapy was discontinued and replaced with bridging low-molecular-weight heparin (LMWH) before and after the ablation, followed by resumption of warfarin at hospital discharge. Although widely adopted throughout the world and endorsed by current guidelines, it was recognized that this approach may result in a higher incidence of bleeding complications, especially at the site of vascular access (24). Several studies have suggested that continuation of therapeutic warfarin could reduce thromboembolic complications without increasing the risk of hemorrhagic complications (16, 25, 26). However, international normalized ratio (INR) levels often fluctuate during warfarin use, and may not be in the optimal therapeutic range in up to >50% of patients (27). Lower or higher INR levels on the day of ablation may increase the risk of complications. Novel oral anticoagulants (NOACs) are used as an alternative to chronic warfarin for stroke prophylaxis in patients with non-valvular AF. They have fast therapeutic effect without need for INR control and obviating the need for bridging heparin.

The registry will collect data about anticoagulation therapy for Phased RFA and correlate it with the peri-procedural thromboembolic events and bleeding.

Endpoint definition:

- Activated clotting time (ACT) during the procedure
- Peri-procedural INR
- Oral anticoagulant therapy/LMWN before, during and after the procedure
- TIA/stroke related to study Phased RFA procedure

Analysis Methods: Oral anticoagulation medication will be displayed before, after and for each procedure and for the FU. Frequency distributions (counts and percentages) will be presented for each point in time and changes in anticoagulation will be displayed. ACT and peri-procedural INR will be displayed by descriptive statistics (n, mean, SD, median, IQR, minimum and maximum). TIA/stroke event rates related to phased RFA procedure during the first three days after procedure will be calculated using Kaplan Meier estimates.

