## 7.3 Categorisations

Variable categorisations will be done and displayed for all variables created for subgroup definitions (number of patients treated with PVAC GOLD solely). Following variable categorisations will be also displayed:

- Age by categorisation 1 [years]: <65, 65-74, ≥75
- Age by categorisation 2 [years]: <65, 65-75, >75, 75-80, >80
- Weight [kg]: ≤60, >60
- Body Mass Index [kg/m^2]: <18.5, 18.5 to <25, 25 to <30, ≥30 (including WHO obesity classes I-III)
- Number of drinks/day > 10
- HAS-BLED: low, medium, high risk (defined at SAP chapter 7.4.2.1)
- CHA2DS2-VASc: low, medium, high risk (defined at SAP chapter 7.4.2.2)
- Previous ablation (none, 1, ≥ 2)
- Previous surgery for AF (none, 1, ≥ 2)
- Hospitalizations due to AF (none, 1, ≥ 2)
- INR before ablation (INR≤1, 0.85<INR<1.27, INR≥1)

All other categories will be determined based on the distribution of the respective baseline data. Additional categorisations can be added, if necessary.

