Unsuccessfulness per vein is considered, if the vein is not isolated or not verified. Percentages for success will be shown per vein for patients treated with PVAC GOLD, all PVs were isolated at the end of the procedure = no and all PVs isolated by using PVAC only = no.

**Table 9:** Procedure success variables from Procedure and AE form

Objective section	Definition (used variables)	Related FID's annotated eCRF (V1.3, V1.4)
Procedure attempt was not declined due to technical issues related to Phased RFA system	Procedure form: Date of procedure Phased RFA procedure successful?  No – Due to AE AE form: Date of AE Was the event related to technical issues?* Related/Possibly related	F20000010 F22000180 F22000190  F30000010 F30000070
Only PVAC catheter(s) used to achieve PVI	Procedure form: Phased RFA catheters used PVAC GOLD (solely) Number of RF applications per patient > 0  Were all PVs isolated at the end of the procedure Were all PVs isolated by using only PVAC	eCRF V1.3/V1.4 F21000010  F20001000 eCRF V1.4 only F22000062  F22000066

All accessible PVs were isolated (entrance and/or exit block confirmation per vein)	Were all accessible PVs isolated at the end of the procedure entrance block and/or exit block Exit block and/or Entrance block	eCRFV1.3/V1.4 F22000010 F22000020 F22000030 F22000040 F22000050 F22000060
---	--	---

\* Precondition: If the documented AE is related to technical issues with Phased RFA system components, the date of the latest procedure must be  $\leq$  date of the AE. For patients with more  $> 1$  procedure, the latest procedure will be the related procedure.

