## 8.8 Graphical analysis

Graphical analysis will be provided for final analysis. The graphs will be created using SAS. Predefined graphical analysis will be done for the following topics and strata. Additional graphical analyses can be carried out after database closure.

**Table 13:** Predefined graphical analysis

Target variable	Analysis method	Patients set or strata
Main objective:  AF re-occurrence by study definition during 12 months  Additional analysis: AF re-occurrence with and without considering the "blanking period" of 90 days  AF re-occurrence up to 14 month (end of FU period) after first documented procedure	Kaplan-Meier estimation (time-to-first-event)	
 
• BAS, FAS, EFAS
 
• AF type
 

Additional objective:  Phased RFA procedure safety	Kaplan-Meier estimation (time-to-first-event)	
 
• FAS
 
• Reason for ablation: index, repeated, re-ablation, left Afl
 

Anticoagulation medication before /during/ after/ at 12months FU	Graphical (stacked) bar analysis	
 
• FAS, EFAS
 
• LAAO implantation
 

Analysis of procedure time by 
 
• Site
 
• Operator
 
	Box-whisker plots	
 
• FAS, EFAS
 

Correlation between Anticoagulation and 
 
• INR
 
• ACT
 
• Stroke
 
	Suitable correlation methods	
 
• FAS
 

Correlation between AF re-occurrence and 
 
• BMI
 
• Age
 
	Suitable correlation methods	
 
• BAS, FAS, EFAS
 

COX regression analysis (SAP chapter 8.1.2)	Forest plot (for HR + CI)	
 
• FAS, EFAS
 

Analysis of DAP - by site	Box-whisker plots	
 
• BAS
 

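### The peri-procedural anticoagulation analysis has no bleeding outcome, its INR classes overlap, and the TIA/stroke row of SAP Table 11 gives no rule for combining its fields

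*SAP*

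**What the plan says.** **Protocol 4.4.3, peri-procedural anticoagulation.** The rationale names two harms: thromboembolic events (1.33%) and major bleeding including tamponade (0.94%). It says anticoagulation data will be collected to "correlate it with the peri-procedural thromboembolic events and bleeding". The endpoint list beneath it covers ACT, INR, anticoagulant use and TIA/stroke. For the last, "TIA/stroke event rates related to phased RFA procedure during the first three days after procedure will be calculated using Kaplan Meier estimates". INR and ACT are summarised as continuous variables.

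**SAP 8.3.3 and Table 11.** The only harm listed is "TIA/stroke related to study Phased RFA procedure". Its definition cell begins "Procedure form: Date of procedure Phased RFA procedure successful? No – Due to AE" and continues with the AE form, giving the AE date and the field identifiers "F30000010 F31000010_2 F31000010_3". Table 7 labels the suffix _2 as stroke. The suffix _3 is not labelled anywhere; from its position I take it to be TIA.

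**SAP 7.3.** The categorised display is "INR before ablation (INR≤1, 0.85<INR<1.27, INR≥1".

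**SAP 8.8, Table 13.** One row is headed "Correlation between Anticoagulation and" and lists INR, ACT and stroke, in the FAS.

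**SAP 8.2.1, Table 7.** The safety objective takes haematoma as a sub-item of F31000010_6 and tamponade as a sub-item of F31000010_8.

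**The concern.** An anticoagulation strategy trades thromboembolism against bleeding, and the protocol says so. An analysis that tabulates only the thromboembolic side cannot describe that trade.

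The protocol also notes that an INR too low or too high on the day of ablation may raise the risk of complications. The INR classes should therefore place each patient once and separate the higher values, and they do neither.

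The TIA/stroke row matters because the events are few. If a programmer took the procedure-success entry as a required condition, strokes found after a successful ablation would drop out of this objective. If it were taken as an alternative source, procedures that failed for an unrelated adverse event would be counted as TIA/stroke.

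**Working it through.** The documents give no event count, precision or power for this objective, so there is no stated figure to reproduce.

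**1. Where bleeding appears**

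| Place | Thromboembolic outcome | Bleeding outcome |
|---|---|---|
| Protocol 4.4.3, rationale | yes | yes |
| Protocol 4.4.3, endpoint list | TIA/stroke | none |
| SAP 8.3.3 and Table 11 | TIA/stroke | none |
| SAP Table 13 | stroke, without TIA | none |
| SAP 8.2.1, Table 7 (safety) | stroke | haematoma, tamponade; not by anticoagulation |
| SAP Appendix D | all AEs pooled | all AEs pooled |

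Appendix C has subgroups for interrupted and continued oral anticoagulation. The tables listed for them are the first procedure, general follow-up and 12-month follow-up, not the AE tables.

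Expected major bleeding events = N × 0.0094:
- N = 800: 7.5
- N = 1000: 9.4

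**2. INR classes**

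Each value is tested against the three written conditions:

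| INR | ≤1 | >0.85 and <1.27 | ≥1 | Classes met |
|---|---|---|---|---|
| 0.85 or less | yes | no | no | 1 |
| above 0.85, below 1 | yes | yes | no | 2 |
| exactly 1.0 | yes | yes | yes | 3 |
| above 1, below 1.27 | no | yes | yes | 2 |
| 1.27 or more | no | no | yes | 1 |

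Percentages can total more than 100%, or depend on the order of programming statements. SAP Table 3 accepts INR up to 9, so everything from 1.27 to 9 shares one class.

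**3. The TIA/stroke row**

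Table 9 pairs the same procedure-form entry with "AE form: Date of AE Was the event related to technical issues" in order to identify a failed attempt, where the entry has a clear purpose. In Table 11 it has none that the text states.

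*AND reading.* Let g be the share of strokes/TIAs that also made the procedure unsuccessful. The documents give no value, so g is an assumption. At the 1.1% stroke/TIA rate the protocol quotes from a European survey, N = 1000 gives 1000 × 0.011 = 11 events, and the row captures 11 × g:

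| g | 0 | 0.10 | 0.25 | 0.50 | 1 |
|---|---|---|---|---|---|
| events captured | 0 | 1.1 | 2.8 | 5.5 | 11 |

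*OR reading.* The protocol's acute success figures of 98.2% and 96.3% imply 1000 × 0.018 = 18 to 1000 × 0.037 = 37 unsuccessful procedures. Those marked as due to an AE, of whatever kind, would be added to the stroke count. The documents do not say how many that is.

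**4. Precision with complete capture**

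- TIA/stroke, 11 of 1000: Clopper-Pearson 95% CI 0.55% to 1.96%.
- Bleeding, 9 of 1000: 0.41% to 1.70%.
- Illustrative power only, since no test is planned: two groups of 500, two-sided 0.05, overall rate p, lower-risk group 2p/(1 + RR). At p = 1.1%, power is 20% for a twofold risk and 38% for a threefold risk. At p = 0.94%, it is 18% and 34%.

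**The case against.** The strongest reply concerns TIA/stroke. A reader might infer that Table 11 limits the outcome to unsuccessful procedures and so leaves almost no events. The documents do not support that:

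- The column lists variables used, and the same cell names the AE-form date and codes.
- Where the SAP wants conditions joined, it says so, as for acute success in 8.3.1. Elsewhere in Table 11 a cell lists alternatives that cannot both be required (LMWH in place of, or on top of, oral anticoagulants).
- Adjudication is required by SAP 7.2.4. Relatedness is taken from the AE form in 8.2.1 and is part of the row's title.
- A reader might also infer that the three-day window has been dropped. SAP 8.3.3 only fails to repeat it. When the SAP overrides the protocol it says so, as in 7.2.3 and 8.1.1.

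All of this stands. What remains is an entry with no stated role in the definition.

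On bleeding, the SAP follows the protocol's own endpoint list, and Appendix D with 8.6.2 compares patients with and without adjudicated AEs. That is fair, but the comparison pools all AE types. The protocol's stated purpose and its endpoint list still disagree, and no justification for leaving bleeding out is given.

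On INR, the classes affect only a categorised display. The INR value itself is a Table 11 variable and its continuous summary is unaffected. That limits the consequence but does not make the classes usable.

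**Conclusion.** Two parts hold on the text alone. The plan has no bleeding-specific outcome for the anticoagulation objective, although the protocol promises one; this concerns about 7.5 to 9.4 major bleeding events at N = 800 to 1000, assuming the protocol's 0.94% applies. The INR classes are not mutually exclusive and do not separate values of 1.27 or more.

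The third part is an ambiguity. Under the AND reading, anything from none to all of about 11 events could be captured, depending on a share the documents do not give. A near-zero count would need that reading and also strokes unrelated to procedural success, neither of which the plan states. It would also be wrong to conclude that anticoagulation cannot be related to stroke at all: Table 13 plans that correlation, and the safety objective also takes TIA/stroke from follow-up forms. Nor does omitting bleeding mean that intensive anticoagulation can only look neutral or better, since a descriptive stroke correlation can go either way.

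The objective is ancillary and descriptive, and any association will stay imprecise after correction. Severity is minor to moderate.

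**What to change.** 1. Add peri-procedural bleeding to SAP 8.3.3, Table 11 and Table 13, and to the protocol's endpoint list or a documented SAP clarification. Use the haematoma sub-item of F31000010_6 and the tamponade sub-item of F31000010_8. The parent codes should not be used, because they also cover fistula, pseudoaneurysm and pericardial effusion. Add TIA beside stroke in Table 13. If bleeding is left out on purpose, say why.
2. Replace the INR classes in SAP 7.3 with mutually exclusive, exhaustive bands that separate the higher values. The sponsor's medical experts should set the cut-offs. Keep the continuous summary.
3. Remove the procedure-success entry from the TIA/stroke row. State that events are adjudicated, procedure-related stroke or TIA from the AE form, whatever the procedural success, analysed in the protocol's three-day Kaplan-Meier window. Confirm that F31000010_3 is the TIA field.
4. Report the event rates with confidence intervals and note that comparisons between strategies are imprecise.

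The cost is SAP wording and a few table rows. No new data are needed.
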